## 5 Study Methods

### 5.1 General Study Design and Plan

The RECEDE–CHF Trial is a single centre randomised, double–blind, placebo–controlled, crossover trial conducted in NHS Tayside to compare the SGLT2 inhibitor empagliflozin 25 mg, to placebo. Participants were randomised to treatment 1, empagliflozin 25 mg/placebo at week 1 for 6 weeks. Then following a two week washout period were randomised to treatment 2, placebo/empagliflozin 25 mg for a further 6 weeks. Renal physiology test days (RPTs) were performed in the first week and the last week of both treatment arms.

### 5.2 Inclusion–Exclusion Criteria and General Study Population

Participants were eligible if they were:

- Aged 18 to 80 years with previously diagnosed Type 2 Diabetes Mellitus
- Diagnosed with NYHA Functional class II–III HF with prior echocardiographic evidence of LVSD
- On stable doses of furosemide, or alternative loop diuretic for at least one month.
- eGFR  $\geq$  45 ml/min
- Had stable HF symptoms for at least three months prior to consent

## Statistical Analysis Plan: RECEDE–CHF trial

- Had stable HF therapy for at least three months prior to consent
- Had not been hospitalised for HF for at least three months prior to consent
- Women of childbearing potential\* (WoCBP) must agree to take precautions to avoid pregnancy throughout the trial and for 4 weeks after intake of the last dose.

Participants were excluded if they:

- Had a diagnosis of chronic liver disease and/or liver enzymes that are twice the upper limit of normal
- Systolic BP of <95mmHg at screening visit
- HbA1c < 6.0%
- were on thiazide diuretics
- were receiving renal dialysis
- had previously had an episode of diabetic ketoacidosis
- had type 1 diabetes mellitus
- had malignancy (receiving active treatment) or other life threatening disease
- were pregnant or lactating women
- had difficulty in micturition e.g. severe prostate enlargement
- had allergy to any SGLT2 inhibitor or lactose or galactose intolerance
- had any past or current treatment with any SGLT2 inhibitor
- had participated in any other clinical interventional trial of an investigational medicinal product within 30 days
- were unable to give informed consent
- Any other reason considered by the physician to be inappropriate for inclusion

### 5.3 Randomisation and Blinding

Participants were randomised to either empagliflozin 25mg/placebo or placebo/empagliflozin 25 mg in a double blind fashion in this crossover study.

The double blind medication (empagliflozin or placebo) was prepared, packaged and labelled by Tayside Pharmaceuticals. Randomisation was carried out by Tayside Pharmaceuticals, using block randomisation using a validated randomisation programme, and will securely backup both the randomisation seed and the randomisation allocation. Tayside Pharmaceuticals use [www.Randomization.com](http://www.Randomization.com) to generate the randomisation lists which they then apply when labelling and packing IMP. This is not specifically named in the Protocol or the Technical Agreement, however it is mentioned in TASC SOP 40 as an example of sources for Randomisation lists. The Clinical Trials Pharmacy, Ninewells Hospital was provided with a copy of the randomisation allocation for the purposes of 24h emergency unblinding.

### 5.4 Study Variables

The primary end point was analysed as the total volume of urine from the 24 hour urine collection at the end of treatment.

Statistical Analysis Plan: RECEDE-CHF trial

Visit	Visit 1* Screening	Visit 2* Baseline/ Randomisation	Visit 3	Visit 4 (Tele Visit)	Visit 5	Two week wash-out period	Visit 6	Visit 7	Visit 8 (Tele Visit)	Visit 9 ****	Visit 10 (Final visit)
	Up to 4 weeks pre visit 2	Day 0	Day 3 (+/-2 days)	Week 3 (+/- 3 days)	Week 6 (+/- 3 days)		Week 9 (+/- 3 days)	Week 9 + 3 days (+/- 2 days)	Week 12 (+/- 3 days)	Week 15 (+/- 3 days)	Week 19 (+/- 7 days)
Height	X										
Weight	X	X	X		X		X	X		X	X
Vital Signs – blood pressure & pulse	X	X	X		X		X	X		X	
Safety Bloods	X	X	X		X		X	X		X	
HbA1c	X				X		X			X	
Research Bloods		X	X		X		X	X		X	
Urine sample	X	X	X		X		X	X		X	
24 hour urinary collection			X		X			X		X	
Renal Physiology Test			X		X			X		X	

Table 1: Trial schedule for RECEDE-CHF

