Participants will undergo detailed renal physiological assessment after 1 week of treatment and end of each treatment period to assess renal physiological parameters to ascertain whether the addition of empagliflozin in conjunction with an intravenous bolus of furosemide improves urine output without any significant adverse consequences. The primary endpoint of the trial is a change in urinary volume in response to furosemide with empagliflozin when compared to placebo.

If our hypothesis is confirmed, it may position SGLT2 inhibitors such as empagliflozin as a mainstay of treatment in participants with DM and CHF. Additionally, it may help to provide an understanding of some of the mechanisms that may provide an improvement in cardiovascular outcome with SGLT2 inhibitors shown in the recently published EMPA-REG¹⁵ trial.

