3.2.2 Urine Tests

Participants will provide a spot urine sample for quantification of albumin/creatinine ratio and protein/creatinine ratio at 4 of the trial days. As well as four 24 hour urinary collections on the days prior to the renal physiological tests days.

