3.2.3 Renal Physiological Tests

Participants will attend the Clinical Research Centre (CRC) on 4 separate trial days (2 while in each arm of the trial). On each trial day, participants will present themselves to the CRC, following an overnight fast. Two days before presenting to the CRC, participants will be required to follow a 2gm sodium and 2L fluid/day controlled diet. A 24-hour urine collection will be made in the 24 hours prior to the day of the renal physiological test. Participants will be asked to take their morning usual medications except their IMP (empagliflozin or placebo) and furosemide (or equivalent loop diuretic).

[figure not shown]
An intravenous cannula will be placed in each arm for subsequent infusion and blood sampling. Bloods will be drawn for measurement of plasma NT-proBNP (a biomarker of wall stress and will be measured as a discovery variable in this proof of concept trial) using standard protocols. Firstly, a 15 ml/kg oral water load will be administered over approximately a 15-minute period. Thereafter, at approximately 30 minute intervals, participants will be requested to void urine until the end of the trial day. The volume of urine passed will be measured and an aliquot stored for later analysis. On each occasion, the volume of urine passed will be measured, and an equal volume of water given to drink. In this way, a steady state diuresis will be established over approximately 3 hours. The last urine collection during this stabilization period will be taken as baseline. Approximately 3 hours after initiation of the test, each participant will receive an oral tablet of either empagliflozin 25mg or placebo. After the seventh urine sample, participants will be given a bolus of IV furosemide at half their total daily dose. Heart rate will be displayed continuously on an ECG oscilloscope and the blood pressure measured approximately every 60 minutes. Venous blood will be obtained at the midpoint of each clearance period for measurement of serum sodium, osmolality and creatinine. At the end of the RPT, light refreshments in the form of tea, coffee or juice with biscuits will be provided. A lunch will then be provided at the CRC.

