9 STATISTICS AND DATA ANALYSIS

9.1 SAMPLE SIZE CALCULATION

9.1.1 POWER CALCULATIONS

Power calculations are based on our previous data in participants with CHF³⁶⁻⁴⁰ as well as more contemporary data.41 The sample size is based on the mean furosemideinduced urinary volume (SD=250). A 20% increase is expected in this parameter following SGLT2 inhibition. This increase in urinary volume is based on published percentage increases in urinary volume in T2D patients that range from 11%-33% depending on the dose of the SGLT2 inhibitor as shown by List and colleagues⁴² in the available data with dapagliflozin (dapagliflozin 2.5 mg: 11% increase in 24-hr urine volume; dapagliflozin 5 mg: 22% 11% increase in 24-hr urine volume; dapagliflozin 10 mg: 24% 11% increase in 24-hr urine volume; dapaqliflozin 20 mg: 27% 11% increase in 24-hr urine volume and dapagliflozin 50 mg: 33% 11% increase in 24-hr urine volume). There is no data of SGLT inhibition together with loop diuretics apart from the previously discussed case report of a diuretic resistant HF patient in whom the fluid overload was successfully treated with the SGLT2 inhibitor, ipragliflozin. The authors reported a striking 50% increase in urinary volume (following treatment with 50 mg daily of oral ipragliflozin for 5 days).34 Based on the above, it was determined that a 20% increase in furosemide induced increase in urinary volume will be reasonable.

With an alpha 0.05 and power of 90%, 22 participants per arm are required, assuming 35% drop out. Since this trial is using an AB/BA crossover design, a total of 34 participants will be required, as each participant will be exposed to both arms of the

trial. The rationale for the high dropout rate, is due to the high intensity renal physiological tests that will occur on 4 occasions for the participants, from 0730 to 1230 we feel that anything less than a 35% drop out rate would be conservative.

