9.2 PROPOSED ANALYSES

9.2.1 STATISTICAL ANALYSIS

Participants will be allocated to treatment groups at random. Descriptive statistics will be calculated for all data and reported as mean (SD) for continuous data and N (%) for categorical data. For statistical evaluation of repeated measurements, analysis of variance will be used. P<0.05 will be taken as the level of statistical significance.

A detailed statistical analysis plan will be prepared during the trial by the trial statistician.

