17 APPENDIX 1: TRIAL SCHEDULE

Visit	Visit 1* Screening	Visit 2* Baseline/ Randomisation	Visit 3	Visit 4 (Tele Visit)	Visit 5	Two week wash-out period	Visit 6	Visit 7	Visit 8 (Tele Visit)	Visit 9 ****	Visit 10 (Final visit)
	Up to 4 weeks pre visit 2	Day 0	Day 3 (+/-2 days)	Week 3 (+/- 3 days)	Week 6 (+/- 3 days)		Week 9 (+/- 3 days)	Week 9 + 3 days (+/- 2 days)	Week 12 (+/- 3 days)	Week 15 (+/- 3 days)	Week 19 (+/- 7 days)
Informed Consent	X										
Inc./Exc. Criteria	Х	Х									
PMH	Х										
Demographics	Х										
Clinical examination	Х						Х				Х
Height	Х										
Weight	Х	X	Х		Х		Х	Х		Х	Х
Vital Signs – blood pressure & pulse	х	х	Х		Х		Х	х		Х	
Safety Bloods	X	X	X		X		X	X		X	
HbA1c	X				X		Х			Х	
Research Bloods		Х	Х		Х		Х	Х		Х	
Genetic Blood Sample		Х									
Additional blood sample		Х			Х		Х			Х	
Urine sample	Х	Х	Х		Х		Х	Х		Х	

Urine Pregnancy Test (WoCBP)	х	Х	Х		Х	Х	Х		Х	X
Ask if participant is pregnant (WoCBP)				Х				Х		
24 hour urinary collection			X		X		X		X	
Renal Physiology Test			Х		Х		Х		Х	
Drug Dispensing		X				Х				
AE assessment		Х	Х	Х	Х	Χ	Х	Х	Х	Х
Record/Review Con Meds	Х	Х	Х	Х	Х	Χ	Х	Х	Х	Х
Drug Compliance Check			Х	Х	Х		Х	Х	Х	

^{*}Visits 1 and Visits 2 combined into one visit where participant is able to stay for results of safety blood tests.

Clinical examination: This will include examination for dehydration via examination of the cardiovascular system including capillary refill, jugular venous pressure and the presence/absence of oedema

Safety Blood sample: U&Es including bicarbonate, LFTs, Glucose, Magnesium, Calcium and Phosphate, Cholesterol, Urate and FBC

Research blood Sample: NT-proBNP, Cystatin C

Genetic Blood Sample: only to be taken if participant consent given.

Additional blood sample: for research purposes, will be stored anonymously for future research use for up to 10 years at the University of Dundee, only to be taken if participant consent given.

Urine sample: for protein/creatinine ration and albumin/creatinine ratio

24 hour urinary collection: Participant will complete this in the 24 hours before visit and bring to visit.

Renal Physiological test: described in Appendix 2

Visit 9**** - if the participant wishes to withdraw prematurely or at the Pl's discretion, all trial procedures will be conducted as though the final visit, if participant agrees.

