### 4.2 Endpoints

The primary outcome for this trial was:

- To assess the effect of empagliflozin versus placebo on urine output

[figure not shown]
The secondary outcomes for this trial were:

- To assess the effect of empagliflozin versus placebo on urinary sodium excretion
- To assess the change in glomerular filtration rate (safety endpoint)
- To assess the change in creatinine (safety endpoint)
- To assess the effect of empagliflozin on protein/creatinine ratio
- To assess the effect of empagliflozin on albumin/creatinine ratio
- To assess the effect of empagliflozin on the renal biomarker, cystatin C.

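### SAP 9 and 9.1 adjust 24-hour urine volume for baselines at visits 2 and 6, where no 24-hour collection is scheduled, and the 90% power in SAP 6 is documented for a different volume

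*SAP*

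**What the plan says.** **The variable.** The protocol's Professional Summary states: "The primary endpoint of the trial is a change in urinary volume in response to furosemide with empagliflozin when compared to placebo". The formal outcome in SAP 4.2, as in Protocol 2.2.1, is looser: "To assess the effect of empagliflozin versus placebo on urine output". SAP 5.4 makes it specific: "The primary end point was analysed as the total volume of urine from the 24 hour urine collection at the end of treatment". Urine volume on the renal physiology test days is analysed by repeated-measures ANOVA under the secondary analyses (SAP 9.2).

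**The collections.** Protocol 3.2.2 plans a fixed number: "As well as four 24 hour urinary collections on the days prior to the renal physiological tests days". Protocol 3.2.3 gives the timing: "A 24-hour urine collection will be made in the 24 hours prior to the day of the renal physiological test". SAP Table 1 places them at visits 3, 5, 7 and 9. A urine sample is also ticked at visits 2 and 6, and the notes to Protocol Appendix 1 give its purpose: "Urine sample: for protein/creatinine ration and albumin/creatinine ratio".

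**The analysis.** SAP 9 compares empagliflozin with placebo at visits 5 and 9, adjusted for the outcomes' baseline values at visits 2 and 6. SAP 9.1 presents the primary result as the treatment difference in change from baseline to final visit. SAP 9.2 treats urinary sodium from the 24-hour collection in the same way.

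**The sizing.** Protocol 9.1.1 and SAP 6 both use furosemide-induced urinary volume with SD 250 and a 20% increase: "With an alpha 0.05 and power of 90%, 22 participants per arm are required, assuming 35% drop out". The total is 34 participants in an AB/BA crossover.

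**The concern.** The analysis sections ask for a quantity that the schedule does not supply. A 24-hour volume at visit 2 or visit 6 is needed both for the adjustment and for the change score, and neither visit has one planned. SAP 5.4 and SAP 9/9.1 therefore describe different primary analyses, of which only one can be run. The plan does not say that the baseline clause lapses for this variable. An analyst might reach for the nearest earlier collections, at visits 3 and 7, which come after dosing has begun.

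The power statement is a second, separate gap. SAP 6 carries over 90% from a sizing on the test-day furosemide response, while SAP 5.4 tests a volume collected before that day's intravenous furosemide. A reader could credit the 24-hour result with a power that the documents never establish for it.

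**Working it through.** **1. Is there a baseline?** Comparing what SAP 9/9.1 need with SAP Table 1:

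| | Visit 2 | Visit 3 | Visit 5 | Visit 6 | Visit 7 | Visit 9 |
|---|---|---|---|---|---|---|
| 24-hour collection | no | yes | yes | no | yes | yes |
| Renal physiology test | no | yes | yes | no | yes | yes |
| Urine sample (ratios) | yes | yes | yes | yes | yes | yes |
| Role in SAP 9 | baseline | – | final | baseline | – | final |

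Neither of the two baseline visits has a 24-hour collection. Protocol 3.2.2 agrees: four collections, each tied to a test day. Taking the furosemide response as primary would not help, because the tests fall on the same four visits and Protocol 3.2.3 takes their baseline within the test day.

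**2. Could visits 3 and 7 stand in?** They fall 3 days (±2) after each period's drug is dispensed, so the preceding 24 hours are mostly or wholly on treatment, to an extent that varies between participants. If a share f of the full effect is already present, a change score shows only (1 − f) of it. For an assumed 400 mL effect, that is 400, 200 or 0 mL at f = 0, 0.5 or 1.

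**3. The plan's own sample size.** 22/(1 − 0.35) = 33.8, which rounds up to 34. This reproduces, so 22 means completers. The 22 itself cannot be reproduced, because the mean to which the 20% applies, the unit, and the type of SD are not stated. If 250 is read as the SD of the within-participant difference, 22 completers with a period term detect 0.727 × 250 = 181.7 at 90% power. At 20%, that implies a mean of about 909, a figure in neither document.

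**4. Power for 24-hour volume.** Two-sided 0.05 (sidedness is assumed), within-participant difference, period term, df = n − 2. Power = P[T(df, λ) > t(0.975, df)], where T is noncentral t and λ = δ√n/σ, with δ the true difference and σ the SD of the within-participant difference.

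- n = 22, df = 20: t = 2.086, and 90% power needs λ = 3.409, so δ = 3.409/√22 × σ = 0.727σ (0.725σ without a period term).
- n = 34, df = 32: t = 2.037, λ = 3.343, so δ = 3.343/√34 × σ = 0.573σ.

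For a 20% effect, 90% power requires σ ≤ 0.20/0.727 = 27.5% of the placebo mean with 22 completers, or 0.20/0.573 = 34.9% with all 34. The σ values below are assumptions, since the documents give none:

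| σ as % of placebo mean | 20 | 25 | 30 | 40 | 50 |
|---|---|---|---|---|---|
| Power, 22 analysable | 99.4% | 94.6% | 84.5% | 60.7% | 43.1% |
| Power, 34 analysable | >99.9% | 99.5% | 96.5% | 80.7% | 61.9% |

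For example, 400 mL with σ = 600 mL (λ = 400√n/600) has 84.5% power with 22 and 96.5% with 34.

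**The case against.** The strongest reply is that a usable analysis is already in the SAP. SAP 5.4 asks for volume at the end of treatment, SAP 9 names visits 5 and 9, and SAP 7.3 includes treatment order. The visit 2/6 clause is written for outcomes in general and works for blood markers and urine ratios. This stands. A reader might infer that no primary analysis is possible, and that would be wrong: only the baseline adjustment and the change-from-baseline presentation fail. It does not remove the conflict, because SAP 9.1 applies the change score to the primary outcome by name.

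On power, the 20% effect comes from published 24-hour volumes (11% to 33%), so the sizing is not foreign to the tested variable, and SAP 6 labels its parameter as furosemide-induced. That also stands, but a relative effect without a mean and SD does not give a power. Nor does this gap bias the estimate or raise the type I error. The 22-completer figure is a planning case. Under SAP 7.2 and 7.4, everyone randomised and dosed is analysed, with imputation where needed, so the effective number could be larger.

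Two further inferences are tempting. One is that the endpoint was switched after results were known. The formal outcome fits either volume, so SAP 5.4 may simply specify it. Protocol 9.2.1 foresaw this: "A detailed statistical analysis plan will be prepared during the trial by the trial statistician". SAP 7.1 places the final analysis after SAP approval. The other is that baseline volumes were never collected; the documents show only that none was scheduled.

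**Conclusion.** The point holds, with limits. As written, the baseline-adjusted and change-from-baseline parts of the primary analysis, and of the 24-hour sodium analysis, cannot be computed from the scheduled data: 0 of 2 baseline visits has the measurement. This rests on the schedules alone and needs no assumed figures.

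The 90% power is not supported for 24-hour volume. A reader might conclude that the trial is underpowered, but the documents do not show that. Over the assumed SDs, power for a 20% effect runs from 43.1% to 99.4% with 22 analysable participants, and from 61.9% to over 99.9% with 34. The range shows how much depends on an unstated SD and supports no direction.

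**What to change.** 1. **SAP 9 and 9.1.** For 24-hour volume and 24-hour sodium, delete the visit 2/6 baseline adjustment and the change-from-baseline presentation, and do not substitute visits 3 and 7. Define the primary analysis as the within-participant empagliflozin minus placebo difference at visits 5 and 9, adjusted for period. With that difference as the outcome, a treatment-order term coded +1/−1 makes the period adjustment. Keep the visit 2/6 baseline for outcomes measured there.
2. **SAP 6.** State that the 90% applies to furosemide-induced volume and not to 24-hour volume. For the latter, give the detectable difference at 90% power as a planning figure: about 0.727 × the SD of the within-participant difference with 22 completers, or about 0.573 × that SD if all 34 are analysable.
3. **Consistency.** Use the same primary variable in the protocol's Professional Summary, SAP 5.4, SAP 6 and SAP 9.1.

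The cost is wording only: no new data are needed, since the visit 5 and 9 collections are already scheduled. The downside is that the 90% claim is withdrawn for 24-hour volume and the primary result becomes an end-of-treatment difference.

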## 6 Sample Size

Power calculations were based on our previous data in participants with CHF as well as more contemporary data. The sample size was based on the mean furosemide-induced urinary volume (SD=250). A 20% increase is expected in this parameter following SGLT2 inhibition. This increase in urinary volume is based on published percentage increases in urinary volume in T2D patients that range from 11%–33% depending on the dose of the SGLT2 inhibitor as shown by List and colleagues in the available data with dapagliflozin (dapagliflozin 2.5 mg: 11% increase in 24-hr urine volume; dapagliflozin 5 mg: 22% 11% increase in 24-hr urine volume; dapagliflozin 10 mg: 24% 11% increase in 24-hr urine volume; dapagliflozin 20 mg: 27% 11% increase in 24-hr urine volume and dapagliflozin 50 mg: 33% 11% increase in 24-hr urine volume). There is no data of SGLT2 inhibition together with loop diuretics apart from a case report of a diuretic resistant HF patient in whom the fluid overload was successfully treated with the SGLT2 inhibitor, ipragliflozin. The authors reported a striking 50% increase in urinary volume (following treatment with 50 mg daily of oral ipragliflozin for 5 days). Based on the above, it was determined that a 20% increase in furosemide induced increase in urinary volume was reasonable.

With an alpha 0.05 and power of 90%, 22 participants per arm are required, assuming 35% drop out. Since this trial is using an AB/BA crossover design, a total of 34 participants was required, as each participant was exposed to both arms of the trial. The rationale for the high dropout rate, was due to the high intensity renal physiological tests that will occur on 4 occasions for the participants, from 0830 to 1330 we feel that anything less than a 35% drop out rate would be conservative.

## 7 General Considerations

### 7.1 Timing of Analyses

The final analysis was performed when all the randomised subjects had completed visit 10 or dropped out prior to visit 10. The final analysis was performed on data transferred to the file RECEDE Master Spreadsheet having been documented as meeting the cleaning and approval requirements of SOP32 and after the finalisation and approval of this SAP document.

